4-{3-[4-cyano-3-(trifluoromethyl)phenyl]-5,5-dimethyl-4-oxo-2-sulfanylideneimidazolidin-1-yl}-2-fluoro-*N*-methylbenzamide. Enzalutamide, 160 mg/day, will be administered as four 40-mg soft gelatin capsules by mouth once daily with or without food.

Reference Therapy, Dose and Mode of Administration:

Placebo capsules, identical in appearance to enzalutamide capsules, will be administered in the same manner as enzalutamide.

Duration of Treatment:

Study drug administration should continue until radiographic progression as specified in the protocol. Investigators are discouraged from obtaining PSA assessments at their local laboratories during the study and from discontinuing a patient's study drug treatment due to PSA rise alone. Initiation of new therapy for prostate cancer (with the exception of cytotoxic chemotherapy, androgen receptor inhibitors, and investigational agents) at the time of radiographic progression will not mandate discontinuation of study drug if the investigator considers continuing study drug to be beneficial. Patients will continue with Enzalutamide after radiographic progression, if continuation of treatment with Enzalutamide seems clinically beneficial.

Statistical Methods:

The primary efficacy analysis of MFS will be conducted using an intent-to-treat population defined as all patients randomly assigned to study treatment. Randomization will be central and treatment allocation will be 2:1. Stratification will be as described in the Methods section. All efficacy analyses will use the intent-to-treat population and incorporate the stratification used at randomization unless otherwise noted. Patients who are randomized and later found to have metastatic disease at enrollment will be censored for time-to-event analyses, and those who receive study drug will be included in all safety analyses.

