3. INVESTIGATIONAL PLAN

3.1. Overall Study Design and Plan:Description

This multinational, phase 3, randomized, double-blind, placebo-controlled, efficacy and safety study will assess the efficacy and safety of enzalutamide versus placebo in approximately 1440 men with nonmetastatic CRPC at approximately 250 study centers. All patients will be required to maintain androgen deprivation during the study, either using a gonadotropin-releasing hormone (GnRH) agonist/antagonist or having a history of bilateral orchiectomy.

Central randomization to enzalutamide or placebo treatments (2:1) will be stratified by the following factors:

- PSA doubling time (< 6 months vs \geq 6 months);
- Baseline use of a bone-targeting agent (yes vs no).

Enzalutamide (160 mg/day) will be administered as four 40-mg soft gelatin capsules by mouth once daily with or without food. Placebo capsules, identical in appearance to enzalutamide capsules, will be administered to patients in the control arm in the same manner.

Study drug administration should continue until radiographic progression. Investigators are discouraged from obtaining PSA assessments at their local laboratories during the study and from discontinuing a patient's study drug treatment due to PSA rise alone. Initiation of new therapy for prostate cancer (with the exception of cytotoxic chemotherapy, androgen receptor inhibitors, and investigational agents) at the time of radiographic progression will not mandate discontinuation of study drug if the investigator considers continuing study drug to be beneficial. Patients will continue with Enzalutamide after radiographic progression, if continuation of treatment with Enzalutamide seems clinically beneficial. Prostate cancer is a multiclonal disease, and a patient with confirmed disease progression may have other clones/foci that may benefit from continued treatment with study drug. In the ongoing, blinded, phase 3 PREVAIL study, approximately 34 of 1715 treated patients (2%) received study drug and antiandrogen or abiraterone after radiographic disease progression.

Initiation of bisphosphonates or other bone-targeting agents for bone health, such as denosumab, is not allowed during the study prior to development of bone metastasis; however, treatment with these agents should continue if initiated at least 4 weeks before enrollment. Standard of care supplementation with calcium and vitamin D is encouraged.

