10.3. Efficacy Analyses

The statistical analysis plan will provide details on additional sensitivity analyses of selected endpoints.

All inferential efficacy analyses will incorporate PSA doubling time (< 6 months vs \geq 6 months) and baseline use of a bone-targeting agent (yes vs no) as the only stratification factors, unless otherwise noted.

The single MFS analysis will be performed after approximately 440 MFS events occur. All secondary endpoints will be evaluated for efficacy at this time. This will include the single analysis of time to PSA progression and time to first use of new antineoplastic therapy as well as the first interim analysis of overall survival. Approximately 135 death events are expected at the time of this analysis. Two additional interim analyses and the final analysis of overall survival are planned after approximately 285, 440, and 596 death events occur, respectively. No additional analyses of other efficacy endpoints are planned at the time of the additional interim and final analyses of overall survival. If an interim analysis of overall survival is statistically significant, it will be reported as the final analysis and no subsequent analyses will be performed.

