2. STUDY OVERVIEW

Protocol MDV3100-14 is a multinational, Phase 3, randomized, double-blind, placebo-controlled efficacy and safety study in patients with nonmetastatic castration-resistant prostate cancer. The primary objective is to determine the efficacy of enzalutamide (formerly MDV3100) (160 mg/day by mouth) compared with placebo as assessed by metastasis-free survival (MFS). Patients will maintain androgen deprivation during the study, either using a gonadotropin-releasing hormone (GnRH) agonist/antagonist or will have a history of bilateral orchiectomy.

A total of 1440 patients will be centrally randomized in a 2:1 ratio to enzalutamide or placebo treatment within each stratum of prostate-specific antigen (PSA) doubling time (< 6 months vs. ≥ 6 months) and prior or current use of bone targeting agents (yes vs. no).

PSA doubling time will be calculated by the sponsor, using the method of Pound et al, 1999.¹ A linear regression model will be used with log-transformed PSA values as the response and the duration of time from the first reference PSA value as the explanatory variable. The slope from the fitted regression line will be used to calculate PSA doubling time in months as follows:

$$\text{PSA Doubling Time (months)} = \frac{\text{LN}(2)*12}{(365.25*\text{Slope of Log (PSA)})}$$

The study consists of screening, double-blind treatment, safety follow-up, and long-term follow-up periods. Radiographic assessments will be performed as described in Appendix 1 approximately every 16 weeks. Patients will continue study drug until radiographic progression. Radiographic progression will be confirmed by independent central radiology review before radiographic imaging stops.

In addition to imaging, the following assessments of prostate cancer status will be made during the study: survival status, PSA values, use of new antineoplastic therapy, pain intensity and interference using the Brief Pain Inventory Short Form (BPI-SF), and quality of life as assessed by the Functional Assessment of Cancer Therapy-Prostate (FACT-P) questionnaire, European Quality of Life-5 Dimensions-5 Levels health questionnaire (EQ-5D-5L) and the European Organization for Research and Treatment of Cancer (EORTC) Quality of Life Questionnaire-Prostate 25 (QLQ-PR25) module.

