9.2. Protocol Deviations

Patients with major protocol deviations will be listed and summarized by treatment group as randomized. Categories of major deviations are as follows:

- Eligibility criteria were not met;
- Developed criteria for discontinuation of study drug but did not discontinue study drug treatment;
- Received excluded concomitant medication;
- Received the wrong treatment or incorrect dose;
- Were incorrectly stratified
- Did not sign informed consent or study-specific procedures were performed before informed consent was signed.

A detailed list of all major protocol deviations will be determined before the study is unblinded and a listing of all major deviations will be provided.

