9.3. Demographics and Baseline Characteristics

The following demographic and baseline characteristics will be summarized by treatment group for all patients in the ITT population and by geographic region:

- Age, race, weight, and body mass index;
- Geographic region (North America, European Union, rest of world);
- Categorized PSA doubling time (< 6 months, ≥ 6 months);
- Baseline use of a bone targeting agent (yes, no);
- Eastern Cooperative Oncology Group (ECOG) performance status;
- Serum PSA;
- PSA doubling time (continuous);
- Quality of life (EQ-5D-5L health score and FACT-P global score);
- Selected laboratory parameters including: testosterone, absolute neutrophil count, platelet count, hemoglobin, total bilirubin, alanine aminotransferase (ALT), aspartate aminotransferase (AST);
- History of cardiovascular disease as defined in Appendix 2.

Listings will be provided for these parameters for all randomized patients.

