4. Compare OS with group sequential testing methodology based on 3 interim analyses and 1 final analysis (described in [Section 9.7.3](#)) at a significance level of 0.05 (if both time to PSA progression in step 2 and time to new antineoplastic therapy in step 3 are declared significant) or 0.03 (if either time to PSA progression in step 2 or time to new antineoplastic therapy in step 3 failed to show significance). The O'Brien-Fleming alpha spending function will be used to determine the stopping boundaries based on the number of events observed at the interim looks to control the overall 2-sided alpha at 0.05 or at 0.03.³

All other efficacy analyses (including sensitivity analyses for primary, and other secondary endpoints) and associated p-values will be deemed exploratory, for which no adjustment for multiplicity will be used.

The key efficacy analyses, order of testing, and multiplicity adjustment rules are summarized in Table 3.

Table 3: Key Efficacy Analyses and Multiplicity Adjustment

Order of Testing	Population	Declare Significant	Statistic	Strata
1. Metastasis-free survival [1]	ITT	p < 0.05	Stratified log-rank test [2]	 PSA doubling time  Prior or current bone targeting agents
	ITT, subgroup [2]	NA		
2. Time to PSA progression	ITT	p < 0.02	Stratified log-rank test	
3. Time to first use of new antineoplastic therapy	ITT	p < 0.02	Stratified log-rank test	
4. Overall survival [3]	ITT	p < 0.05 or p < 0.03 [4]	Stratified log-rank test	

ITT: intent-to-treat; NA: not applicable; PSA: prostate-specific antigen.

1. MFS is the primary analysis.
2. The MFS subgroup analysis will be performed with an unstratified log-rank test.
3. Three interim analyses and 1 final analysis are planned for OS, details of each analysis are provided in [Section 9.7.3](#).
4. If both time to PSA progression and time to first use of new antineoplastic therapy are declared significant, OS will be tested at a 0.05 significance level; otherwise, OS will be tested at 0.03.

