9.7.2. Primary Efficacy Analysis of Metastasis-Free Survival

MFS will be evaluated for the ITT population. MFS is defined as the time from randomization to the first date of radiographic progression (assessed by blinded ICR) or death on study (death within 112 days of treatment discontinuation without evidence of radiographic progression), whichever occurs first. Radiographic assessments from both

scheduled and unscheduled assessments will be used to determine events in the primary analysis. For patients not known to have had radiographic progression or death at the time of the analysis data cutoff, MFS time will be censored at the date of the last available scan before the analysis data cutoff date for the purposes of analysis. Patients who were randomized but later confirmed to have metastatic disease before randomization by ICR assessment or patients with no postbaseline tumor assessment information will be censored on the date of randomization. Patients who initiate antiandrogen receptor agents (eg, bicalutamide, flutamide, or nilutamide) without evidence of metastasis as per ICR review will not be censored for the primary MFS analysis. The details of the censoring rules are provided in [Appendix 1](#).

Significance Level

A 2-sided alpha of 0.05 will be preserved for the primary endpoint of MFS and key secondary endpoints using the testing strategy outlined in [Section 9.7.1](#). The primary endpoint of MFS and all secondary endpoints will be analyzed when approximately 440 MFS events based on ICR occur. See [Section 5](#) for additional details.

Methodology

MFS will be compared between the 2 treatment groups using a stratified log-rank test. The strata will be PSA doubling time (< 6 months vs. ≥ 6 months) and prior or current use of a bone targeting agent (yes vs. no). Kaplan-Meier curves will be used to estimate the distribution of duration of MFS. The 50th percentile of Kaplan-Meier estimates will be used to estimate the median duration of MFS. A 2-sided 95% confidence interval will be provided for this estimate. In cases where the median is not reached as of the data cutoff, the 25th percentile and its 2-sided 95% confidence interval will be provided. The progression and censoring reason will also be summarized for each treatment arm.

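### Do the protocol and the SAP stratify the confirmatory tests by different bone-targeting-agent factors?

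*SAP*

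**What the plan says.** Protocol Section 3.1 gives the second randomization factor as "Baseline use of a bone-targeting agent (yes vs no"; the Synopsis agrees. For inferential efficacy analyses, Protocol Section 10.3 names PSA doubling time and "baseline use of a bone-targeting agent (yes vs no) as the only stratification factors, unless otherwise noted". The Synopsis, under Statistical Methods, adds that efficacy analyses "incorporate the stratification used at randomization unless otherwise noted".

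SAP Section 2 says men are randomized within strata of PSA doubling time and "prior or current use of bone targeting agents (yes vs. no". The Strata column of SAP Table 3 (Section 9.7.1) lists "Prior or current bone targeting agents", and the MFS methodology in Section 9.7.2 uses "prior or current use of a bone targeting agent (yes vs. no". In Section 9.7.3, time to PSA progression and time to new antineoplastic therapy take the MFS strata by reference. The OS text there says only that the log-rank test is stratified, so Table 3 supplies its strata.

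The SAP also has the protocol's label: Section 9.3 tabulates "Baseline use of a bone targeting agent (yes, no", and the MFS subgroups in Section 9.7.2 use the same variable name. Section 9.2 counts patients who "Were incorrectly stratified" among major deviations.

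**The concern.** In ordinary language the labels describe different sets of men. One who used an agent and stopped before baseline is a yes under the SAP's strata label and a no under the protocol's. Inclusion criterion 5 concerns men receiving an agent and does not exclude those who stopped. SAP Section 7.1 classifies agents by drug name only, with no timing rule. Only one factor can have driven the randomization, so unless the labels are synonyms, one document misnames it.

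At stake is pre-specification. If two stratum variables were available for a confirmatory test, the p-value and hazard ratio would depend on which was picked. The MFS analysis, the single analyses of the other two key secondary endpoints and the first OS interim fell at the 28 June 2017 cutoff, after which patients were unblinded (SAP Sections 2 and 8). The OS looks at about 285, 440 and 596 deaths remain. A deviation category for incorrect stratification also presupposes a known definition of the factor.

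**Working it through.** **1. Where the labels appear.**

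| Use | Protocol | SAP |
|---|---|---|
| Randomization factor | baseline use (Synopsis, 3.1) | prior or current use (2) |
| Strata of the tests | baseline use (10.3) | prior or current use (Table 3, 9.7.2; by reference in 9.7.3) |
| Baseline table, MFS subgroup | not applicable | baseline use (9.3, 9.7.2) |

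Neither document randomizes on one factor and tests on another. An analyst following the SAP meets one named factor for every key stratified test, described there as the randomization factor. In the SAP's baseline and subgroup lists, baseline use stands directly after PSA doubling time, just as prior or current use does where the strata are listed. That fits one variable with two labels, though it does not prove it.

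**2. The plan's own event figure.** Schoenfeld's formula with hazard ratio 0.72, two-sided 0.05, 90% power and 2:1 allocation (SAP Section 5):

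events = (1.960 + 1.282)² / [(2/3)(1/3)(ln 0.72)²] = 10.51 / (0.2222 × 0.1079) ≈ 438.2, so 439.

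With 440 events the power is 90.1%, so the planned 440 is reproduced. The formula does not involve the stratum label.

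**3. Validity.** Both candidate variables are fixed before randomization. Stratifying the log-rank test by either compares like with like and introduces no bias. What remains is how often the two tests would disagree.

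**4. Size by simulation.** The documents do not say how many men used an agent at baseline or stopped one earlier. Assumptions: N = 1440, 2:1; 10% users at baseline; 75% with PSA doubling time under 6 months; hazard ratio 1.0 to 1.5 for agent use; uniform accrual over 36 months. Both tests were run on the same simulated data.

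MFS at 440 events, two-sided 0.05, randomized on baseline use, 2000 trials per cell. Paired entries are baseline-use strata / prior-or-current strata.

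| Men reclassified | Agent HR | Type I error, % | Power at HR 0.72, % | Decisions differ, null / alternative, % |
|---|---|---|---|---|
| 29 (2%) | 1.0 | 4.80 / 4.95 | 92.0 / 91.95 | 0.15 / 0.35 |
| 29 (2%) | 1.5 | 5.30 / 5.30 | 91.55 / 91.85 | 0.50 / 0.50 |
| 72 (5%) | 1.0 | 4.75 / 4.60 | 91.75 / 91.80 | 0.45 / 0.45 |
| 72 (5%) | 1.5 | 5.85 / 5.80 | 91.75 / 91.50 | 0.55 / 1.55 |
| 144 (10%) | 1.0 | 4.15 / 4.55 | 91.65 / 91.20 | 0.50 / 0.75 |
| 144 (10%) | 1.5 | 5.55 / 5.55 | 91.15 / 91.45 | 1.00 / 1.20 |

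The Monte Carlo standard error of a 5% rate is √(0.05 × 0.95 / 2000) ≈ 0.49 points, so the extremes of 4.15% and 5.85% lie 0.85 / 0.49 ≈ 1.7 standard errors from 5%.

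A second simulation (4000 trials per scenario, 1%, 5% or 10% reclassified, randomization on either variable, 0.2% monthly dropout) covered MFS and the remaining OS looks at hazard ratio 0.77:

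| Analysis | Nominal level | Decisions differ, all scenarios |
|---|---|---|
| MFS, 440 events | 0.05 | 0.30% to 1.32% |
| OS, 285 deaths | 0.002 | 0.38% to 1.95% |
| OS, 440 deaths | 0.018 | 0.38% to 2.85% |
| OS, 596 deaths | 0.044 | 0.27% to 2.02% |

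The OS figures are per look, not cumulative. With 1% reclassified (0.01 × 1440 ≈ 14 men) the ranges are 0.3% to 0.6% for MFS and 0.3% to 1.2% for the OS looks. The largest power difference was 0.51 points. MFS type I error averaged 5.2% with baseline-use strata and 5.1% with prior-or-current strata.

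**5. Which scenario is nearest.** The screening medication record covers ongoing drugs and those stopped in the preceding 28 days (Protocol Table 1), and the prior-medication record covers 4 weeks (Protocol Section 7.1). Agents started at least 4 weeks before enrollment are to be continued. On that record few men could be prior-only users, so 1% is closer than 5% or 10%. It is still an assumption.

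**The case for a change.** The best argument for a change is that the protocol's permission to depart from the randomization strata covers only the choice of analysis strata. SAP Section 2 describes the randomization itself, and it does so differently from the protocol version on which the SAP says it is based. The SAP uses both labels, so a reader of it alone could take them for two variables. With patients unblinded and OS looks to come, the strata should rest on a documented source rather than on a choice made at analysis. Checking the randomization system's field would cost little.

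Part of this stands. The labels are not equated, one document may misname the factor, and no explicit rule covers a man entered in the wrong stratum. The rest is weaker. The Synopsis already ties efficacy analyses to the strata used at randomization, and SAP Section 9.1 tabulates patients by those factors, so the recorded values exist and will be reported. The sponsor can judge incorrect stratification against the system field even though a reader of these documents cannot. SAP Section 7.1 has the agents classified blinded and bars changes after unblinding, which limits latitude over which drugs count.

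**Conclusion.** The wording differs, but two different factors are not shown, and no change to the plan follows. The natural analysis uses the strata recorded at randomization, as the protocol's general rule implies, for the remaining OS looks as for the completed tests. Even if the labels did denote different variables, both tests would be valid: type I error stays near 5% and power moves by at most about 0.5 points. Decisions would differ in roughly 0.3% to 1.2% of trials per analysis with 1% of men affected, and in no more than 2.9% at any look in the most extreme assumed scenario.

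These sizes rest on assumed agent-use prevalence and prognostic effect, and on single assumed values for the PSA-doubling-time share and the accrual pattern; the SAP itself assumes increasing accrual. The validity of either test does not depend on them. Harmonizing the label would be tidy, but it would not improve any stated figure, the power, the error control or the trial's answer.

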9.7.3. Analyses of the Key Secondary Efficacy Endpoints

Time to PSA progression

PSA progression is defined according to Prostate Cancer Working Group 2 (PCWG2) guidelines. Time to PSA progression is defined as the time from randomization to the date of first PSA value demonstrating progression, which is subsequently confirmed. Patients without confirmed PSA progression at the time of analysis will be right censored at the date of last PSA assessment before the analysis data cutoff date for the purposes of analysis.

For patients with PSA declines at week 17, the PSA progression date is defined as the date that a $\geq 25\%$ increase and an absolute increase of ≥ 2 $\mu\text{g/L}$ (2 ng/mL) above the nadir is documented, which is confirmed by a second consecutive value obtained at least 3 weeks later.

For patients with no PSA declines at week 17, the PSA progression date is defined as the date that a $\geq 25\%$ increase and an absolute increase of ≥ 2 $\mu\text{g/L}$ (2 ng/mL) above the baseline is documented, which is confirmed by a second consecutive value at least 3 weeks later.

As step 2 of the testing strategy described in [Section 9.7.1](#), the ITT analysis for the time to PSA progression endpoint will be conducted with 0.02 alpha level (2-sided), if and only if, enzalutamide is assessed to be statistically superior to placebo for the primary endpoint of MFS. See [Section 5](#) for additional details.

A stratified log-rank test will be used to compare the treatment groups with the same strata as in the time to MFS analysis described in [Section 9.7.2](#).

Time to First Use of New Antineoplastic Therapy

Time to first use of new antineoplastic therapy is defined as the time from randomization to first use of new antineoplastic for prostate cancer. Patients not starting treatment with a new antineoplastic therapy at the time of analysis will be right censored at the date of last assessment before the analysis data cutoff date for the purposes of analysis.

As step 3 of the testing strategy described in [Section 9.7.1](#), the ITT analysis for the time to first use of new antineoplastic therapy endpoint will be conducted with 0.02 alpha level (2-sided), if and only if, enzalutamide is assessed to be statistically superior to placebo for the primary endpoint of MFS and the secondary endpoint of time to PSA progression. See [Section 5](#) for additional details.

A stratified log-rank test will be used to compare the treatment groups with the same strata as in the time to MFS analysis described in [Section 9.7.2](#).

At the time of the third interim and at the final analysis of OS, this endpoint will be updated and provided as an exploratory analysis.

Overall Survival

OS is defined as the time from randomization to death from any cause. For patients who are alive at the time of the analysis data cutoff, OS time will be censored at the last date the patient was known to be alive or analysis data cutoff date, whichever is earlier. Patients with no postbaseline survival information will be censored on the date of randomization.

As step 4 of the testing strategy described in [Section 9.7.1](#), the ITT analysis for the OS endpoint will be conducted with 0.05 (or 0.03 if either time to PSA progression or time to new antineoplastic therapy fails to show significance) alpha level (2-sided), if and only if, enzalutamide is assessed to be statistically superior to placebo for the primary endpoint of MFS. Three interim analyses and 1 final analysis for OS are planned. The data cutoff date will be applied to achieve the approximate number of deaths at each of these analyses.

Depending on the outcome of the time to first use of new antineoplastic therapy endpoint, the total type I error rate across the interim and final analyses will be controlled at 0.03 or 0.05 with the O'Brien-Fleming alpha spending function. The significance level will be fixed at

0.001 for the first interim analysis. For the other overall survival analyses, the significance levels will be recalculated based on the actual number of events at each analysis using the O'Brien-Fleming method, using the remaining type I error rate (0.029 or 0.049 depending on the outcome of the time to PSA progression and time to first use of new antineoplastic therapy endpoint). If an interim analysis of overall survival is statistically significant, it will be reported as the final analysis and no subsequent analyses will be performed. The approximate number of events and corresponding significance level at each analysis based on this methodology are provided in Table 4.

Table 4: Type I Error Spending for the Overall Survival Analyses

Analysis	Number of Death Events [1]	Significance Level	
		Error Rate: 0.03 [2]	Error Rate: 0.05 [3]
First interim	135	0.001	0.001
Second interim	285	0.001	0.002
Third interim	440	0.009	0.018
Final	596	0.026	0.044

[1] Approximate number of targeted events.

[2] Will be used if either time to PSA progression or time to first use of new antineoplastic therapy endpoint fails to show significance. The significance level will be fixed at 0.001 for the first interim analysis. For the other analyses, the significance levels will be recalculated based on the actual number of events at each analysis using the O'Brien-Fleming method.³

[3] Will be used if both time to PSA progression and time to first use of new antineoplastic therapy endpoint show significance. The significance level will be fixed at 0.001 for the first interim analysis. For the other analyses, the significance levels will be recalculated based on the actual number of events at each analysis using the O'Brien-Fleming method.³

The first interim analysis will be conducted at a 0.001 significance level at the time of the primary MFS analysis. A stratified log-rank test will be used to compare the 2 treatment groups. The number and percentage of death events in each treatment group will be summarized with Kaplan-Meier curves of overall survival with the hazard ratio and its 95% CI.

A second interim analysis is planned after approximately 285 death events are observed. A stratified log-rank test will be used to compare the 2 treatment groups at a 0.002 or 0.001 (depending on the outcome of time to PSA progression and time to new antineoplastic therapy tests) significance level (exact significance level will be calculated based on exact number of events using the O'Brien-Fleming alpha spending function). The number and percentage of death events in each treatment group will be summarized with Kaplan-Meier curves of overall survival with the hazard ratio and its 95% CI.

A third interim analysis is planned after approximately 440 death events are observed. A stratified log-rank test will be used to compare the 2 treatment groups at a 0.018 or 0.009 (depending on the outcome of time to PSA progression and time to new antineoplastic

therapy tests) significance level (exact significance level for this analysis will be calculated based on exact number of events using the O'Brien-Fleming alpha spending function). The number and percentage of death events in each treatment group will be summarized with Kaplan-Meier curves of overall survival with the hazard ratio and its 95% CI.

The final analysis is planned after approximately 596 death events are observed. A stratified log-rank test will be used to compare the 2 treatment groups at a 0.044 or 0.026 (depending on the outcome of time to PSA progression and time to new antineoplastic therapy tests) significance level (exact significance level for this analysis will be calculated using the O'Brien-Fleming alpha spending function). The number and percentage of death events in each treatment group will be summarized with Kaplan-Meier curves of overall survival with the hazard ratio and its 95% CI. If an interim OS analysis is statistically significant, it will be reported as the final analysis and no subsequent analyses will be performed.

At the time of the final analysis of OS, subgroup analyses will be conducted using the same analysis methods as for the subgroup analyses of MFS described in Section 9.7.2.

At the final analysis of OS, to adjust the treatment crossover effect, a sensitivity analysis of OS using Rank-Preserving Structural Failure Time Model (RPSFTM) method will be performed. Additionally, the inverse probability of treatment weighting (IPTW) method may also be performed as an exploratory analysis as appropriate.

